5.2 Eligibility criteria

5.2.1 Inclusion criteria

Key inclusion criteria, which apply to all the above ongoing studies, are the following:

1. Patients enrolled in NureCombo, SURE-01, and SURE-02 clinical trials or candidates to radical cystectomy as per routine clinical practice.
2. Histopathologically-confirmed UC.
3. ECOG performance status 0-1.
4. Clinical stage T2-T4aN0M0, assessed by thorax-abdomen CT scan and combined whole-body FDG-PET scan plus bladder mpMRI.

 I.R.C.C.S. Ospedale San Raffaele	AIRC Investigator Grant (IG) 2022 27746	Data: 02/02/2023 Versione: 01
--	---	----------------------------------

5. The patient accepts to undergo RC as per clinical practice.
6. Ineligibility to receive cisplatin-based neoadjuvant chemotherapy based on poor renal function (glomerular filtration rate according to Cockroft-Gault formula <60 ml/min) OR refusal to receive neoadjuvant cisplatin-based chemotherapy

5.2.2 Exclusion criteria

Patients unwilling to participate to the study and unwilling to sign the informed consent.

6 PROCEDURES

There are no special procedures scheduled for this study in addition to those already planned within the NureCombo, SURE-01, SURE-02, and the routine clinical practice.

7 STUDY VARIABLES

All the clinical variables of the patients will be collected from the CRF of the corresponding studies. The same body of information will be collected from paper source data for the patients included in the standard-of-care radical cystectomy cohort as reported in the list of variables in attachment.

8. HANDLING OF ADVERSE EVENTS AND ADVERSE REACTIONS

Adverse events will be treated as reported in the reference studies (SURE-01, SURE-02, NURE-COMBO) and in accordance with clinical practice for the cohort doing clinical practice cystectomy, as there are no procedures performed *ad hoc* for the present study.

9. DATA MANAGEMENT

The data of patients included in the study-corresponding trials are already gathered and collected within electronic or paper source, depending on the trial. For the standard-of-care arm the data will be collected via paper source of clinical charts.

10. HANDLING OF BIOLOGICAL SAMPLES

Tumor tissue samples used for biomarker analyses will be obtained from archival, paraffin-embedded blocks that are stored at the Department of Pathology of IRCCS Ospedale San Raffaele or in other institutions/hospitals, according to the routine clinical practice. Therefore, there is no study-specific legislation regulating the storage and handling of such samples. Regarding the liquid biopsy samples, these samples will be collected and stored, limited to the duration of study analysis, at the Laboratory of [name] a the Laboratory of Cellular Immunology Unit of IRCCS San Raffaele Hospital. At the end of the study samples will be dismissed and destroyed and no further storage is expected. Regarding the imaging repository, the imaging data are collected, stored and anonymized according to the routine practice.

 I.R.C.C.S. Ospedale San Raffaele	AIRC Investigator Grant (IG) 2022 27746	Data: 02/02/2023 Versione: 01
--	---	----------------------------------

11. STATISTICAL ANALYSES

The study is aimed to provide a proof-of-principle to inform further prospective studies aimed at establishing new biomarkers of response to neoadjuvant therapies in MIBC.

There will not be a formal statistical comparison of findings between the study cohorts, as the treatment characteristics and the overall design will prevent doing such comparisons. Therefore, statistical analyses will be applied within each trial arm to measure the effects between biomarker cohorts.

The primary endpoint of interest for each of the clinical trials is the pathological complete response (pT0N0). Patient, tumor characteristics and pT0N0 rates will be compared between subgroups by using χ^2 tests and two-sided Wilcoxon rank-sum tests.

Descriptive statistics with medians and IQR, or frequencies and proportions were presented as appropriate. Fischer's exact and Wilcoxon rank-sum tests will be used to analyze the associations between laboratory or clinical variables, e.g., molecular subtypes or single biomarker tests, and the pathological response. Kaplan-Meier curves and log-rank tests will be used to analyze the relapse-free survival (RFS) and overall survival (OS) outcomes in relation to gene signatures, molecular subtypes, or single gene expressions. Continuous-scale analyses will evaluate single-gene or signatures expression, and will be analyzed in Cox proportional hazards models that will include biomarker and the clinical T-stage.

Logistic regression models will analyze pre- and post-pembrolizumab VI-RADS against pT \leq 1N0 and pT0N0 pathological response. VI-RADS scores were dichotomized between 0-3 and 4-5.

All statistical tests will be two-sided, and will be reported with a significance level of 0.05. Analyses will be performed in R v3.4.1 (R Foundation, Vienna, Austria).

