3 DESIGN OF THE STUDY

This is both a prospective and retrospective study aimed to evaluate multiple cohorts of patients already included in ongoing prospective clinical trials (SURE-01, SURE-02, NURE-COMBO), plus an additional cohort of patients prospectively receiving upfront radical cystectomy as routine clinical practice.

As most of the clinical trials representing the core-business of the study are already recruiting patients, we will retrospectively retrieve and analyze the tumor and blood samples of these patients, and in parallel we will prospectively collect the material of newer patients.

 I.R.C.C.S. Ospedale San Raffaele	AIRC Investigator Grant (IG) 2022 27746	Data: 02/02/2023 Versione: 01
--	---	----------------------------------

[figure not shown]
The retrospective part of the study will be based on the analysis of tumor and blood samples analyses dating back to January 2022, date of the start of the enrolment of the ongoing clinical trials that are the core business of this project.

MIBC tumor tissues will be collected from MIBC patients undergoing neoadjuvant therapy. We will acquire pre-treatment tissue from TURBT and post-treatment tissue from residual disease at RC (from patients not achieving complete pathologic response).

The umbrella of neoadjuvant studies representing the source of tumor and blood samples will consist of the following studies (Figure 1):

- In SURE-01, 56 eligible patients will receive neoadjuvant treatment with 10 mg/kg sacituzumab govitecan IV, on days 1, 8, of each 21 day cycle, for a total of 4 cycles.
- In SURE-02, pembrolizumab will be administered in combination with sacituzumab govitecan on day 1, every 21 days, at the standard dose of 200 mg intravenously. A total of 4 cycles is planned before surgery and the study sample size is 48 patients.
- In Nure-Combo trial 29 patients will receive 4 cycles of preoperative nivolumab 360 mg intravenously, every 3 weeks, plus nab-paclitaxel 125 mg/m² intravenously, on days 1 and 8, every 3 weeks.
- Curative-intent RC + pelvic lymph node dissection will be planned at the time of study inclusion to be done within 4 weeks of the last dose of study drug.
- After surgery, in SURE-01 patients will be managed with surveillance or adjuvant chemotherapy depending on the pathological response, according to the protocol.

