 I.R.C.C.S. Ospedale San Raffaele	AIRC Investigator Grant (IG) 2022 27746	Data: 02/02/2023 Versione: 01
--	---	----------------------------------

- Task 2.2 (Months 1-60): whole transcriptome expression analyses.

We will rely on an established collaboration with Veracyte scientists, extensively pursued in SURE-01 trial.^{4,6,9,10}

Specimen collection and sample processing will be conducted using Veracyte (former Decipher Biosciences Laboratory, San Diego, CA, USA), a clinical-grade whole transcriptome assay, as described in our previous work.^{6,10}

Unsupervised consensus clustering: For unsupervised clustering analysis (R package ConsensusClusterPlus), normalized expression data will be pre-processed by filtering low-variance genes, selecting the 2,000 genes with the highest median absolute deviation. The expression clustering analysis will be performed by consensus partitioning around medoids (PAM) approach, using Pearson correlations as the similarity metric, the Ward algorithm for clustering, running 1,000 iterations with 0.875 random fraction of samples used in each iteration (pItem) and 0.95 random fraction of gene features used in each iteration (pFeature).

Classification of tumors into molecular mRNA subtypes: To assign tumors to the consensus bladder cancer and The Cancer Genome Atlas (TCGA) 2017 molecular subtypes,²³ we will download and apply the centroid-based models as described previously. The Decipher subtypes will be assigned by identifying neuroendocrine (NE)-like patients and then classifying the remaining tumors using Seiler *et al.* model.²⁴ The Lund (2012)²⁵ model will be applied as previously described.²⁶ The consensus classifier will provide the standard classification of the NE-like subtype.²⁶

Gene expression analysis: Heatmaps and boxplots will be used to visualize differences between samples from unsupervised consensus clusters (CCs). Sample purity will be calculated by the ESTIMATE algorithm and the other signature score calculations have been previously described.^{6,9}

- Task 2.3 (Months 1-60): Immune-monitoring by multiparametric flow cytometry

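### If all molecular subtypes of a classifier are compared in one ordinary log-rank test within arms of 29, 48 and 56 patients, the stated 0.05 is not held when several subtypes are small and unequal

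*Protocol*

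**What the plan says.** Section 11 plans survival plots together with formal tests: "log-rank tests will be used to analyze the relapse-free survival (RFS) and overall survival (OS) outcomes in relation to gene signatures, molecular subtypes". It fixes the unit of analysis: "statistical analyses will be applied within each trial arm to measure the effects between biomarker cohorts". It also fixes the error rate: "All statistical tests will be two-sided, and will be reported with a significance level of 0.05". No exact or permutation version of the log-rank test is named.

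Section 3 sets the arm sizes: "In SURE-01, 56 eligible patients will receive neoadjuvant treatment"; for SURE-02, "the study sample size is 48 patients"; and "In Nure-Combo trial 29 patients will receive 4 cycles".

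Task 2.2 in Section 3 names several classifiers. One step is "To assign tumors to the consensus bladder cancer and The Cancer Genome Atlas (TCGA) 2017 molecular subtypes". Another is "The Decipher subtypes will be assigned by identifying neuroendocrine (NE)-like patients and then classifying the remaining tumors". The Lund 2012 model is applied as well. The Protocol does not say how many classes each classifier yields, how patients are expected to spread over them, how many relapses or deaths are expected per arm, or whether all classes enter a single test.

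**The concern.** The ordinary log-rank test for K groups refers its statistic to a chi-square distribution with K-1 degrees of freedom. That approximation needs a reasonable number of expected events in every group. If 29 to 56 patients are spread unevenly over five or six classes, the rarest classes may hold very few patients, with about one expected event or fewer. A single early event in such a class can then produce a large statistic by chance.

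At stake is the false-positive rate of each single subtype test for RFS or OS. This is separate from the number of tests run, so a multiplicity adjustment would not cure it. Where the excess arises it comes mainly from the rarest subtypes, and a signal there could misdirect the prospective studies that this work is meant to inform.

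**Working it through.** **Inputs from the Protocol.** Arm sizes 56, 48 and 29 (Section 3). Log-rank test, within arm, two-sided 0.05 (Section 11).

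**Assumptions, because the Protocol gives no figure.**
- Number of subtypes: five or six, with two and three for comparison.
- Shares: several unequal splits, listed in the table.
- Event fraction: 20-50%. The Introduction puts recurrence above 40% within two years, but for patients in general and not for these arms, so 40% is only an anchor.
- All classes are compared in one test.

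**How thin the rarest class becomes.** Expected patients = n × share; expected events = n × share × event fraction. At 40% events:
- Share 5%, n=29: 29 × 0.05 = 1.45 patients; 1.45 × 0.40 = 0.58 events.
- Share 5%, n=56: 56 × 0.05 = 2.80 patients; 2.80 × 0.40 = 1.12 events.
- Share 3%, n=48: 48 × 0.03 = 1.44 patients; 1.44 × 0.40 = 0.58 events.
- Share 8%, n=29: 29 × 0.08 = 2.32 patients; 2.32 × 0.40 = 0.93 events.

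**Test statistic.** With U the vector of observed minus expected events over K-1 of the groups and V its hypergeometric covariance matrix, X² = U′V⁻¹U. The null is rejected when X² exceeds the 95% point of chi-square, with degrees of freedom one fewer than the number of groups that have expected events.

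**Simulation under the null.** Exponential survival, identical in all subtypes; uniform staggered-entry censoring; subtype counts drawn at random from the assumed shares; 24,000 trials per cell for the table. Near a size of 10% the simulation standard error is √(0.10 × 0.90 / 24,000) = 0.0019, or about 0.2 percentage points. The statistic agreed exactly with a standard software routine on three test data sets.

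Share of null trials rejected at nominal 5% (40% events; range over 20-50% events in brackets):

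| Assumed shares (%) | n=29 | n=48 | n=56 |
|---|---|---|---|
| 35/25/20/12/8 | 11.0 (9.1-12.2) | 8.9 (7.5-9.2) | 8.0 (7.1-8.7) |
| 35/35/19/6/5 | 13.9 (10.9-14.4) | 12.0 (10.2-12.6) | 11.3 (9.6-11.7) |
| 30/22/18/14/10/6 | 13.8 (10.8-15.1) | 10.4 (8.7-10.7) | 9.6 (8.5-10.2) |
| 35/24/15/15/8/3 | 14.7 (11.0-15.6) | 12.1 (10.6-13.1) | 11.8 (10.1-12.3) |

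The table spans 7.1% to 15.6%. Outside it, the result moves with the assumptions in both directions: about 6% for a mild imbalance at n=56 with 15-25% events and fixed subtype counts, and above 20% in some cells for an extreme 60/20/8/5/4/3 split.

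**Fewer groups.**
- Three groups: about 5-8%, depending on the split.
- Two groups at 50/50 or 75/25: about 4-6%.
- Two groups at 85/15, 40% events: 6.2% (n=29), 5.6% (n=48), 5.6% (n=56).
- Two groups at 90/10, 40% events: 7.0%, 6.1%, 5.8%.

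**Check of the two remedies.**
- Permutation log-rank (800 data sets, 399 permutations each, 40% events), five subtypes 35/35/19/6/5 and six subtypes 35/24/15/15/8/3: 4.9% and 5.6% (n=29), 5.1% and 4.6% (n=48), 5.0% and 4.0% (n=56). Simulation error is about 2 × √(0.05 × 0.95 / 800) = 0.015, or 1.5 points. The ordinary test on the same data sets gave 11-16%.
- Ordinary log-rank after leaving out subtypes with fewer than 5 patients in the arm (three to six groups, 20% and 40% events, all three arm sizes): 4.2-6.7%.

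**The case against.** The strongest reply is that the defect depends on things the Protocol does not say. Section 11 does not state that all classes go into one test. Contrasting one subtype with the rest fits its wording equally well, and then the size is near 5%: comparing the largest subtype with all others gave 3.9-5.8% in every arm. Nor does the Protocol give class counts or shares. It says that NE-like tumours are identified first, not that they are few. This objection stands, and it is why the point is conditional.

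A second reply is that the reference distribution and the handling of sparse classes are often settled in a statistical analysis plan, which is not shown here. That has weight. But Section 11 itself fixes the test, the within-arm unit and the 0.05 level. It also already names Fisher's exact test for subtypes against pathological response, so it makes a small-sample choice for one outcome and not for the other.

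A third reply is that little hangs on these results. The study is a proof of principle, the main interest is pathological response, and no decision is tied to RFS or OS by subtype. This lowers the severity. It does not make 0.05 the true error rate.

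Finally, replacing the test is not the only remedy: a minimum subtype size does almost as well. That is accepted below.

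**Conclusion.** The point holds conditionally. If all classes of a classifier are compared in one ordinary log-rank test within an arm, and there are five or six unequal subtypes with 20-50% events, the false-positive rate is about 7-16% instead of 5%: typically 9-15% at n=29 and 8-13% at n=48 and 56. The number of subtypes, their shares, the event fraction and the single joint test are all assumptions.

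A reader might infer that every subtype p-value for RFS or OS will be wrong, that chance findings will be at least twice as frequent as stated, or that some subtypes will certainly hold only a handful of patients. The documents do not support this. With two groups that are not extremely unequal the level is about right, with three groups the excess is modest, and even among the assumed five- and six-class splits some cells fall short of a doubling (for example 7.1-8.7% for 35/25/20/12/8 at n=56).

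Severity: consider, because these are exploratory survival analyses in a proof-of-principle study.

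**What to change.** Add one sentence to Section 11: log-rank comparisons across more than two molecular subtypes within an arm use a permutation reference distribution, for example 10,000 permutations of the subtype labels within that arm. This restores about 5%. It costs a few lines of R code and no new data. It assumes that censoring is unrelated to subtype within an arm, which should be stated.

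Alternatively, keep the ordinary log-rank test, include only subtypes with at least 5 patients in the arm, and show smaller ones descriptively. The size is then about 5-7%. The price is that the rarest subtypes get no formal test. Either option is enough by itself.

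Whichever is chosen, Section 11 should also say whether all classes of a classifier are tested jointly or one class is contrasted with the rest, since that decides whether the problem arises.

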A comprehensive characterization of the tumor-associated immune compartment in MIBC is currently lacking but would have important implications for predicting determinants of response and resistance to both immunotherapy and other therapies in MIBC. We expect to compare peripheral and local immune contexture in MIBC patients from 3 unique cohorts receiving different neoadjuvant therapies, and compare the findings with untreated tumor models. The findings generated in this study could potentially be expanded to significantly larger MIBC datasets currently available, comprised of whole tissue gene expression data with limited to no immunological data.

Overall, we anticipate identifying patterns of peripheral immune response and/or tumor immune infiltration with prognostic and predictive significance in the context of neoadjuvant therapy, which provides the opportunity to study patient-matched pre- and post-therapy specimens from the same anatomic site allowing deeper characterization of features specifically associated with treatment exposure itself. Furthermore, by integrating the immune signature obtained with transcriptome analyses and IHC with radiological imaging data we could potentially provide investigators with a useful tool to inspire newer bladder-sparing approaches in the near future. The value of the clinical data source relies mainly in the use of advanced treatments that anticipate the use of the best therapeutic options available at present (CPI-chemotherapy combination, ADC and CPI+ADC combination).

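### Section 11 adjusts every expression Cox model for clinical T-stage alone, without separating TURBT tissue from residual tumour; for residual tumour this leaves ypT/ypN unaccounted for

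*Protocol*

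**What the plan says.** Section 11 of the protocol uses Kaplan-Meier curves and log-rank tests to "analyze the relapse-free survival (RFS) and overall survival (OS) outcomes in relation to gene signatures, molecular subtypes, or single gene expressions". It continues: "Continuous-scale analyses will evaluate single-gene or signatures expression", to be analysed in "Cox proportional hazards models that will include biomarker and the clinical T-stage". No pathological T or N stage is named, no tissue time-point is given, and no time origin is stated. Testing is two-sided at 0.05, and analyses are made within each trial arm.

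Section 3 has two tissue sources: pre-treatment TURBT tissue, and "post-treatment tissue from residual disease at RC (from patients not achieving complete pathologic response". Its Phase 3 text expects to identify "patterns of peripheral immune response and/or tumor immune infiltration with prognostic and predictive significance in the context of neoadjuvant therapy", and says the setting offers "patient-matched pre- and post-therapy specimens from the same anatomic site allowing deeper characterization of features specifically associated with treatment exposure itself". The Introduction describes transcriptome changes between matched pre- and post-treatment samples in the earlier pembrolizumab work, including a new post-treatment mRNA subtype.

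Section 5.2.1 restricts baseline stage to T2-T4aN0M0. Section 2 defines response from ypT and N stage in the cystectomy report, so pathological stage will be on record for every operated patient.

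**The concern.** Clinical T-stage is assessed before treatment and, because all patients are clinically N0, carries no nodal information. Once the bladder has been removed, the stage that competes with a residual-tumour marker as an explanation of relapse is ypT/ypN. Patients without a complete response can range from non-muscle-invasive residual disease to locally advanced or node-positive disease, and immune or stromal expression may well vary along that range. Section 3 adds a second route: in SURE-01, management after surgery depends on the pathological response.

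A residual-tumour signature that only reflects residual stage could therefore be significant beside clinical T-stage and be read as carrying information of its own. The study exists to inform later prospective biomarker studies, and one of those could be built on a costly proxy for a stage that the pathologist already reports.

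**Working it through.** The protocol gives no power, event or sample-size figure for the Cox models, so there is nothing to reproduce. The check asks how often a marker with no effect of its own would reach p<0.05.

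**Number of patients with residual tumour.** Arm sizes are from Section 3. The 42% pT0N0 rate is from the earlier single-agent pembrolizumab trial in the Introduction and serves only as an illustration; those were not the present regimens.

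- SURE-01: 56 × 0.58 = 32.5, run at 32
- SURE-02: 48 × 0.58 = 27.8, run at 28
- Nure-Combo: 29 × 0.58 = 16.8, run at 17

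At the 29% response rate also quoted there, the factor is 0.71 and the counts are about 40, 34 and 21.

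**First simulation** (1,500 runs per setting; everything below is assumed).

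- Pathological stage s takes three equally likely levels: 0 = residual ypT<2N0, 1 = ypT2N0, 2 = ypT3-4 or N+.
- Hazard = HR^(s − 1), with HR per level 1.5, 2.0 or 3.0.
- Marker = ρ(s − 1)/0.8165 + √(1 − ρ²)·e, with e standard normal. The divisor √(2/3) = 0.8165 is the SD of s. The marker does not enter the hazard.
- Latent correlation of clinical with pathological stage is 0.3. About 45% of patients have an event, which is 0.45 × 17 ≈ 8, 0.45 × 28 ≈ 13 and 0.45 × 32 ≈ 14 events.
- Wald test at |z| > 1.96.

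Percentage of runs with p<0.05 for the marker; each cell is clinical T-stage only / pathological stage added:

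| HR per level, ρ | n = 17 | n = 28 | n = 32 |
|---|---|---|---|
| 1.5, 0.3 | 4.8 / 5.2 | 6.5 / 5.1 | 6.2 / 5.4 |
| 1.5, 0.6 | 7.0 / 6.1 | 10.8 / 7.8 | 10.9 / 5.8 |
| 2.0, 0.3 | 6.3 / 4.5 | 7.0 / 5.4 | 8.4 / 5.1 |
| 2.0, 0.6 | 12.4 / 6.0 | 17.8 / 6.0 | 21.4 / 6.5 |
| 2.0, 0.8 | 18.2 / 5.7 | 30.8 / 5.9 | 34.9 / 6.7 |
| 3.0, 0.8 | 33.1 / 5.7 | 56.2 / 6.2 | 64.5 / 6.6 |

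With ρ = 0 (control), the clinical-stage model gives 4.5-6.9%. With pathological stage added, all settings at these sizes lie between 4.2% and 7.8%. The Monte Carlo standard error near 5% is √(0.05 × 0.95/1,500) = 0.6 points.

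**Second simulation** (1,500 runs per setting, likelihood-ratio test). Stage has two levels, and pathological stage replaces clinical T-stage instead of joining it. Assumed: 45% of residual cases are ypT3-4/N+, with HR 3-4; baseline hazard 0.25 per year; follow-up 1-2.5 years; clinical T3-4a in 55% versus 35% by residual stage.

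- Marker 0.8 SD lower in ypT3-4/N+: 12.5-14.6% at n = 28 and 12.0-17.1% at n = 32 with clinical T-stage, against 6-7% with pathological stage.
- Marker 0.5 SD lower: 7.6-9.2% against 5.7-6.8%.
- n = 17: both models run at 9-14%.

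The moderate range of 12-21% joins the second simulation at 0.8 SD with the first at HR 2.0, ρ = 0.6.

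**Limits.** In the first simulation the added term is the true three-level stage; a two-level term could leave part of the confounding if risk also differs within the lower group. At n = 17 the two simulations disagree on whether the adjusted test holds its level, and in the first one up to about 9% of fits with pathological stage did not converge.

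**The case against.** The strongest reply is that the protocol never says residual-tumour expression will enter the Cox models. Its stated use of matched specimens is to characterise features linked to treatment exposure, and for TURBT markers clinical T-stage is a sensible covariate. This stands, and it makes the point conditional. Equally, nothing restricts the Cox sentence to TURBT tissue, and residual tumour is collected under a prognostic aim.

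Second, tissue time-point and time origin may be set out in an analysis plan that is not shown. That is fair for those two details. The covariate, however, is not left open: the protocol fixes it for all continuous expression analyses.

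Third, a marker that tracks residual stage really is associated with relapse, so a significant result is not a false finding of association. This stands too. The error would be to read it as information beyond stage.

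Fourth, a true resistance marker may act through residual stage, and adjusting for ypT/ypN alone could hide it. This is a good reason not to substitute one model for the other outright, and the fix keeps both.

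A reader might infer that stage-tracking markers will be reported as prognostic. The documents and the figures do not support that: at the per-arm sizes the rate runs from about 5% to 65%, mostly below 50%, on effect sizes the protocol does not give. Larger rates obtained by pooling the three trials do not apply, since Section 11 analyses within each arm. Nor does the point extend to blood markers, because the Cox sentence concerns expression.

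**Conclusion.** The point holds in conditional form. As worded, Section 11 applies one pre-treatment covariate to expression from either tissue source. If residual-tumour expression is modelled, clinical T-stage does not remove confounding by ypT/ypN, and a pure proxy for residual stage can pass as independently prognostic.

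The size depends on assumptions outside the documents: how closely the marker tracks stage, how strongly stage predicts outcome, and the number of residual cases and events. The excess over 5% is almost nil when tracking is weak (HR 1.5, ρ = 0.3). Under moderate assumptions the rate is about two and a half to four times nominal in the two larger arms (12/5 = 2.4; 21/5 = 4.2). It is larger still under strong assumptions. With pathological stage in the model it stays at about 4-8%. In Nure-Combo, about 17 residual patients and 8 assumed events cannot support an adjusted test either way.

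**What to change.** In Section 11, state the following:

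- For expression measured on baseline TURBT tissue, the Cox covariate is clinical T-stage, as now. Pathological stage is not added routinely, since it arises after treatment and may lie on the path from marker to outcome.
- For expression measured on cystectomy tissue, time is counted from cystectomy. Any claim of independent prognostic value rests on a Cox model with the marker and pathological stage (ypT3-4 or N+ versus lower) instead of clinical T-stage. The model without pathological stage is reported beside it, so that signal acting through residual stage stays visible.
- In Nure-Combo, results for cystectomy-tissue markers are descriptive only.

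The cost is a few sentences and one additional model per post-treatment marker. No new data are needed, because ypT/ypN comes from the cystectomy report. The model with pathological stage has no more terms than the one now planned, which matters with about 28-32 residual patients per arm.
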